7 TRIAL DESIGN

This is a multi-centre, randomised controlled study of participants recruited via primary care, and the community, who wish to reduce their smoking, but have no immediate plan to quit. Following written consent and completion of baseline measures, 900 participants will be randomly allocated in a 1:1 ratio to either the intervention or control arm. Randomisation will follow permuted blocks, stratified by recruitment site, and the score from the 2-item Heaviness of Smoking Index (HSI) [74].

7.1 Trial schema

7.2 Study personnel

The study will be led at each of the four collaborating University sites (Plymouth University, Nottingham University, St George's University of London, and Oxford University) by a local Principal Investigator.

All study personnel undertaking home visits will be asked to comply with their employers' lone working policy. All staff working with study participants will be required to complete Disclosure and Barring Service (DBS) checks, as they may be working with vulnerable individuals.

Health trainers will be part of the research team and trained to support participants in the intervention. They will be line managed by the site PI and receive training and supervision by a member of the lead site research team.

7.3 Docmail®

Sites will be allowed to use Docmail® during the study for mailing out study related correspondence to participants.

7.4 Primary outcome

Carbon monoxide (CO) verified prolonged abstinence over 6 months

We will use guidance provided by Aveyard *et al* (2009) [75] on floating prolonged abstinence. Study participants who report abstinence on the 3 month mailed survey (which is confirmed by face to face CO expired air assessment) and then again self-report abstinence (and not having smoked even a puff since the 3 month assessment) on the 9 month mailed survey (which is again confirmed by CO expired air assessment), will be identified as having prolonged abstinence over at least 6 months.

The CO monitor used in this study is a Bedfont Micro CO monitor. The CO measurement involves the participant holding their breath for 10-15 seconds, and then blowing into the monitor. The carbon monoxide value in parts per million (ppm) is shown with values below 10 ppm indicating abstinence. The reading at each recruitment site will be reported remotely into the on-line PenCTU data management system. The CO monitor will be regularly calibrated to ensure accurate measures.

7.5 Secondary outcomes

Point prevalence CO verified abstinence at 3, 9 and 15 months post baseline

Only those reporting abstinence by mailed survey at 3 and 9 months will be contacted for CO verification. Only those abstinent at 9 months will be followed up at 15 months by mailed questionnaires and if abstinent by face-to-face assessment of expired CO.

Self-reported smoking and use of aids to reduce/quit smoking

Study participants will be asked to self-report the number of cigarettes smoked and type of nicotine product, i.e. pipes, cigars and roll your own. The same formula used in the EARS pilot study will be used to convert amount of loose tobacco into number of cigarettes [1].

Questions to capture use of e-cigarettes and NRT (nicotine replacement therapy) products

Physical activity

Questions at baseline, 3 and 9 months will assess self-reported 7-day physical activity recall. A sub set of all participants in the TARS study will be invited to wear an accelerometer for a 7 day period during the study. The accelerometer, and instructions for use will be mailed to selected participants at the 3 month time point from CTU, along with the 3 month questionnaire booklet. The accelerometer is waterproof, and is worn continuously for 7 days. At the end of the 7 days the participant should return the accelerometer to the CTU in the freepost envelope provided.

Self-reported height and weight - Body Mass Index (BMI)

At baseline, 3 and 9 months participants will be asked to self-report their height and weight. The questions will be part of the questionnaire booklet mailed to participants from CTU at baseline, 3 and 9 months. Based on the weight and height reported we will derive a measure of BMI.

Health related quality of life (EQ-5D-5L & SF-12)

EQ-5D-5L

This is described in section 19.1.

SF-12

The SF-12 is a 12-item, patient-reported survey of patient health, consisting of twelve questions [70]. In this study participants will be asked to complete the SF12 as part of the questionnaire booklet mailed to them from CTU at baseline, and then at 3 months follow-up and 9 months follow-up.

Health economic outcomes

Health service utilisation and costs, including smoking related costs

Process measures

The following process measures will also be assessed as part of the self-report questionnaire booklets issued to all participants by CTU at the baseline and 3 months:

- Importance and confidence in smoking reduction and cessation
- Importance and confidence in being physically active
- Availability of support to reduce smoking and increase physical activity
- Use of physical activity for smoking regulation
- Planning to change smoking
- Planning to change physical activity
- Self-monitoring of smoking
- Self-monitoring of physical activity
- Urge & strength of urge to smoke

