6 AIMS AND OBJECTIVE

The overarching research question is whether in addition to the usual standard support, a client-centred intervention with behavioural support to reduce smoking and promote physical activity, for smokers wishing to reduce smoking with no immediate plans to quit (but who may be open to the notion of quitting), can increase CO-confirmed prolonged abstinence at 9 months post baseline (i.e. 6 months post intervention) compared to standard support alone, and whether such an intervention is cost-effective.

The aims of the trial are as follows:

[figure not shown]
- To determine whether the additional behavioural support for an intervention promoting smoking reduction and increasing physical activity, compared to support as usual (SAU), significantly increases the proportion of participants who achieve prolonged abstinence at 9 months post baseline as confirmed by the concentrations of their expired CO.
- To determine whether the intervention, compared to SAU, increases the proportion of participants who reduce self-reported cigarette smoking by at least 50% at 3 and 9 months post baseline compared to baseline smoking levels, while quantifying the use of licenced nicotine containing products (LNCPs) and e-cigarettes.
- To determine whether the intervention, compared to SAU, increases the proportion of participants who achieve CO-confirmed prolonged abstinence at 15 months post baseline (i.e., 12 months post intervention).
- To determine whether the intervention, compared to SAU, increases self-reported physical activity at 3 and 9 months post baseline, and accelerometer assessed physical activity at 3 months post baseline.
- To determine whether the intervention, compared to SAU, improves quality of life (SF 12, EQ-5D-5L), weight and cigarette cravings at 3 and 9 months post baseline.
- To estimate the additional resource use and costs of delivering the intervention and to estimate
 the differences in health and social care service utilisation and the related costs between
 intervention and SAU at 9 months post baseline.

- To estimate the cost-effectiveness of the intervention compared with SAU at (i) 9 months (incremental cost per unit change in abstinence rate, and cost per quality adjusted life year [QALY] gained) and (ii) over a longer term / lifetime horizon (incremental cost per life year saved, per QALY gained) extrapolating beyond the trial using a previously developed decision-analytic model to estimate future costs and benefits.

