A shopping voucher will be mailed to all participants upon CTU receipt of the completed 3 month questionnaire booklet. No additional incentive will be provided for selected participants to return the accelerometer.

Expenses to attend the expired CO assessment session will also be provided.

10.2 9 month follow-up assessments

The 9 month assessments will be mailed to participants in the form of a questionnaire booklet, with a cover letter, and freepost return envelope. An opportunity will be given for participants to complete the questionnaire booklet over the telephone with a member of the local research team if they would prefer.

The 9 month questionnaire booklet contains questions relating to the following:

- Smoking behaviour
- Self-reported physical activity (7-day physical activity recall)
- Use of e-cigarettes and NRT (nicotine replacement therapy) products
- Health related quality of life (EQ-5D-5L & SF12)
- Self-reported height and weight (BMI)
- · Health service utilisation and costs, including smoking related costs
- · Serious adverse event reporting

Participants who self-report that they have quit will be invited to attend a face-to-face assessment which will include the following additional assessments:

- Self-reported prolonged abstinence (since last quit attempt, with date, if relevant)
- Expired carbon monoxide (CO) measurement

A shopping voucher will be mailed to participants upon CTU receipt of the completed 9 month questionnaire booklet.

Expenses to attend the expired CO assessment session will also be provided.

10.3 15 month follow-up assessments

The 15 month assessments will be mailed only to participants who are confirmed quitters at 9 months. The assessments will be in the form of a questionnaire booklet, with a cover letter, and freepost return envelope. An opportunity will be given for participants to complete the questionnaire booklet over the telephone with a member of the local research team if they would prefer.

The 15 month questionnaire booklet contains questions relating to the following:

- Smoking behaviour
- Use of e-cigarettes and NRT (nicotine replacement therapy) products

Only participants who have been confirmed as quitters at 9 months and self-reported quitting at 15 months will be invited to participate in the following 15 month assessments:

- Self-reported prolonged abstinence (since last quit attempt, with date, if relevant)
- Expired carbon monoxide (CO) measurement

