10.6 Schedule of delivery

	Screening &	Day	Intervention	Month	Month	Month
	Baseline	0	Week 1 – 8*	3	9	15
			(Intervention			
			arm only)			
Eligibility check	Х					
Consent	Х					
Randomisation		Х				
Demographics	Х					
Importance and confidence in smoking reduction and	Х			Х		
cessation						
Importance and confidence in being physically active	Х			Х		
Availability of support to reduce smoking and increase	Х			Х		
physical activity						
Use of physical activity for smoking regulation	Х			Х		
Self-reported physical activity (7-day physical activity	Х			Х	Х	
recall)						
Planning to change smoking	Х			Х		
Planning to change physical activity	Х			Х		
Self-monitoring of smoking	Х			Х		
Self-monitoring of physical activity	Х			Х		
Urge & strength of urge to smoke	Х			Х		
Use of e-cigarettes and NTR (nicotine replacement	Х			Х	Х	Х
therapy) products						
Health related quality of life (EQ-5D-5L & SF12)	Х			Х	Х	
Self-reported weight & height (BMI)	Х			Х	Х	
Health service utilisation and costs,	Х			Х	Х	
Serious adverse events (self-reported)				Х	Х	
Self-reported prolonged abstinence (since quit attempt,				Х	Х	Х
with date, if relevant)						
CO expired air confirmed abstinence (<10ppm)**				Х	Х	Х
Accelerometer (7 days)				Х		

^{*}If a smoker wishes to quit at any time during the 8 week intervention period, they will be offered 6 weeks of additional support from the Health Trainer, a meeting with a specialist advisor in a stop smoking service, and pharmacological and behavioural support.

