10.7 End of trial

Participants who are self-reported quitters at 9 and 15 months will complete the study at the 15 month time point. All other participants will complete the study at the 9 month time point. The trial itself will end when all assessments that are expected to be conducted are completed.

^{**}Participants reporting prolonged abstinence from the point of quitting in the first 3 months of the study will be telephoned and invited to provide a sample of expired CO at a face-to-face visit with a site researcher. Participants with confirmed CO abstinence at 9 & 15 months will be contacted, and if continuing to report abstinence will be telephoned and invited to provide a sample of expired CO at a face-to-face visit with a site researcher.

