17.2.4 Analysis of secondary outcomes

Between-group comparisons will be undertaken at 3 and 9 months post baseline for all available outcome measures, and only prolonged abstinence rates at 15 months. Analysis will use multivariable logistic regression to compare these secondary outcomes between allocated groups, with adjustment for the stratification factors [site, HSI], as well as important baseline covariates (i.e. age, gender, socio-economic status, level of smoking, recent quit attempts).

The between-group comparisons of continuous outcomes (e.g. daily cigarettes smoked, minutes of MVPA) will be reported as mean differences together with 95% confidence intervals, unless the outcomes are substantially skewed. Multi-variable linear regression will be used to compare continuous variables between allocated groups, with adjustment for the stratification factors, important baseline covariates, and baseline outcome values, where relevant.

Sensitivity analysis will examine the potential influence of participants lost to follow-up under varying assumptions. Further sensitivity analysis may be undertaken if any marked imbalance between allocated groups is seen in important baseline characteristics, by further adjustment for such baseline characteristics in the multi-variable models detailed above.

Finally, we will conduct exploratory mediational analysis to determine if any effect of trial arm on the primary outcome was mediated by changes in smoking, physical activity, from baseline to 3 months. We will also examine if changes in smoking and physical activity are mediated by changes in various secondary outcomes (eg, importance and confidence to reduce smoking/increase physical activity; self-monitoring and goal setting; cravings)

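### The protocol names 15-month point prevalence abstinence and 9-month cravings as results, but its own assessment schedule collects the data for neither

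*Protocol*

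**What the plan says.** **15 months.** Section 7.5 of the protocol names the outcome as "Point prevalence CO verified abstinence at 3, 9 and 15 months post baseline" and, directly beneath it, limits who is seen: "Only those abstinent at 9 months will be followed up at 15 months by mailed questionnaires". Section 10.3 agrees: "The 15 month assessments will be mailed only to participants who are confirmed quitters at 9 months". Section 10.7 closes off everyone else: "All other participants will complete the study at the 9 month time point". The Section 4 summary also lists CO-verified abstinence at 15 months, without saying whether point prevalence or prolonged abstinence is meant.

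Section 6 states the 15-month aim as CO-confirmed prolonged abstinence, explained as 12 months after the intervention. Section 17.2.4 restricts the 15-month comparison to "only prolonged abstinence rates at 15 months". Under 17.2.5 the 15-month wave goes ahead only if the 9-month result is statistically significant.

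Footnote ** to the schedule of delivery (printed under 10.7) says: "Participants with confirmed CO abstinence at 9 & 15 months will be contacted", the purpose of the contact being an invitation to give an expired-CO sample.

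**Cravings.** One aim in Section 6 is to compare quality of life, "weight and cigarette cravings at 3 and 9 months post baseline". The row "Urge & strength of urge to smoke" in the schedule (10.6) is marked at baseline and Month 3 only.

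**The concern.** Point prevalence at a time point is the proportion of all randomised participants who are abstinent then. It needs everyone's status at that time, or a defensible rule for those not seen. Here the people not seen at 15 months are excluded by design: every participant still smoking at 9 months. Some may have stopped by month 15, and the schedule cannot find them.

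If the outcome in 7.5 were reported as named, with the uncontacted counted as smokers (the rule that 17.2.2 applies to missing primary-outcome data), late quitters would be misclassified in both arms and the ratio between the arms would be distorted. The result would appear only after a significant 9-month comparison, because the wave is conditional on it.

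The cravings problem is simpler. A stated aim would have no 9-month data, and data not collected at 9 months cannot be recovered afterwards.

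**Working it through.** **The plan's own figure.** Full enumeration of the two-sided Fisher exact test at 5% versus 11% and alpha 0.05 gives power 0.9003 at N = 900 and 0.8995 at N = 898. The stated 900 reproduces, and nothing below alters it.

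**15 months: what can be observed**

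1. Those contacted at 15 months are the participants abstinent at 9 months (7.5, 10.3). The gate is worded as abstinent in 7.5, confirmed in 10.3 and self-reported in 10.5 and 10.7. None of these wordings admits a participant who is smoking at 9 months.
2. Observable: abstinent at both 9 and 15 months. Not observable: smoking at 9 months and abstinent at 15 months.
3. Point prevalence at 15 months is the sum of these two groups, so it cannot be obtained.
4. Prolonged abstinence to 15 months requires abstinence at 9 months, so nobody who could count is lost. The outcome named in Section 6 and 17.2.4 is deliverable.

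**Direction of the error if point prevalence were reported anyway.** The documents give no late-quit rate, so this is an illustration on assumptions: 9-month abstinence of 5% (control) and 11% (intervention), a proportion r = 0.70 of these still abstinent at 15 months, and the same late-quit rate q among 9-month smokers in both arms.

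- Seen by the schedule: p × r, i.e. 0.05 × 0.70 = 3.5% and 0.11 × 0.70 = 7.7%. The risk ratio is 2.20 and the risk difference 4.2 points, whatever q is.
- True value: p × r + (1 − p) × q.

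| q | Control | Intervention | True risk ratio | True risk difference |
|---|---|---|---|---|
| 1% | 4.45% | 8.59% | 1.93 | 4.14 points |
| 2% | 5.40% | 9.48% | 1.76 | 4.08 points |
| 5% | 8.25% | 12.15% | 1.47 | 3.90 points |

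Missed quitters per arm are 450 × (1 − p) × q: about 4.3 control and 4.0 intervention at q = 1%, and 21.4 and 20.0 at q = 5%. The numbers missed are nearly equal, so the difference hardly moves. They are added to unequal bases, so the ratio does. Section 17.2 reports odds ratios and relative risks, which are ratio measures.

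**Footnote \*\*.** At 15 months it is circular, because CO confirmation at 15 months is made the condition for being invited to give the 15-month CO sample. At 9 months it is narrower than 10.2, which invites every participant who self-reports having quit.

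**Cravings: the passages side by side**

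- Section 6: cravings compared at 3 and 9 months.
- Section 7.5: urge and strength of urge, the only craving measure named, is a process measure taken at baseline and 3 months.
- Sections 8.7 and 10.1: the baseline and 3-month booklets list urges as an item of their own, apart from smoking behaviour.
- Section 10.2: the 9-month booklet lists seven topics, and urges are not among them. Its smoking-behaviour topic cannot be assumed to cover them, given the separate listing in the other two booklets.
- Section 10.6: marked at baseline and Month 3 only.

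**The case against.** The strongest reply is that the planned 15-month analysis is sound. Section 17.2.4 limits it to prolonged abstinence, Section 6 asks for the same, and the restricted contact stands openly beside the outcome in 7.5. That is right, and it confines the point to the outcome as named. A reader might infer that the planned 15-month comparison is itself biased; the documents do not support that.

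A reader might also try to size the problem from the planning rates: 450 × 5% + 450 × 11% = 22.5 + 49.5 = 72 abstinent, leaving 900 − 72 = 828 not abstinent at 9 months, to which a late-quit rate is applied. This fails. The 5% and 11% are planning rates for the primary outcome, confirmed abstinence at both 3 and 9 months. People who quit after month 3 can be abstinent at 9 months without being among the 72. So 828 is too high for those not contacted and 72 too low for those carried forward. The illustration above borrows the same rates, so it shows direction and scale dependence only, not an estimate.

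Nor do the documents say that controls catch up after 9 months. The overstatement of the ratio follows from equal late-quit rates, which is an assumption.

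It may also be argued that the 15-month prolonged outcome has two possible numerators, because the mailing takes in people who quit after month 3. This is minor: the 12-months-post-intervention wording in Section 6 points to month 3 to month 15, and mailing a wider group than the numerator is no contradiction.

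On cravings, the objection that a single phrase in one aim is out of line with 7.5, the booklets and the schedule is fair. Reference in 17.2.4 to all available measures softens the analysis text, but the aim still promises a comparison for which no data are planned.

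**Conclusion.** Both contradictions are real and lie within the protocol. They concern who is contacted and what is asked, so an analysis plan could not supply the missing data. Section 7.5 names a 15-month outcome that the schedule cannot measure. Section 6 names a 9-month cravings comparison for which nothing is collected.

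The consequence is limited. The primary outcome, N = 900 and the 15-month prolonged-abstinence analysis all stand. The harm arises only if a 15-month point prevalence is reported with uncontacted participants scored as smokers. Under equal late-quit rates in the two arms, relative measures would then be too large and the risk difference nearly unchanged. How much too large depends on late-quit and retention rates that the documents do not give. The correction is still worth making, because it concerns a named secondary outcome and a stated aim and costs almost nothing.

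**What to change.** - **Section 7.5:** list point prevalence at 3 and 9 months only. Name the 15-month outcome as CO-confirmed prolonged abstinence from month 3 to month 15, in line with the 12-months-post-intervention wording in Section 6. If wanted, report 9-to-15-month abstinence among those who quit after month 3 separately.
- **Section 4:** make the 15-month entry consistent with this.
- **Footnote \*\* in 10.6:** align it with 10.2 and 10.3 on who is invited for CO measurement.
- **Cravings:** either add the urge items to the 9-month booklet and the schedule before the 9-month mailings begin, or limit the aim in Section 6 to 3 months.

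The cost is protocol wording and, if the first cravings option is chosen, a few more questionnaire items at 9 months. Only that option has a deadline.

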9.2 Support as usual

Participants allocated to both arms of the trial will receive guidance for smoking reduction and cessation, including web links to what is offered at local level, or paper versions of this information. In the current financial climate and without clear evidence of benefit and a clear pathway of care, it

is unlikely that there will be much support for smoking reduction as described as usual care. Given the rapidly changing public health environment we do not propose to request approval for this guidance or amendments from the REC if and when changes occur to what is offered locally to prevent unnecessary delays to the trial but will be happy to forward versions as appropriate.

10 Follow-up Assessments – all participants

10.1 3 month follow-up assessments

The 3 month assessments will be mailed to participants in the form of a questionnaire booklet, with a cover letter, and freepost return envelope. An opportunity will be given for participants to complete the questionnaire booklet over the telephone with a member of the local research team if they would prefer. A subset of study participants will also receive an accelerometer by post, and instruction sheet at the 3 month time point.

The 3 month questionnaire booklet contains questions relating to the following:

- Smoking behaviour
- Importance and confidence in smoking reduction and cessation
- Importance and confidence in being physically active
- Availability of support to reduce smoking and increase physical activity
- Use of physical activity for smoking regulation
- Self-reported physical activity (7-day physical activity recall)
- Planning to change smoking
- · Planning to change physical activity
- Self-monitoring of smoking
- · Self-monitoring of physical activity
- Urge & strength of urge to smoke
- Use of e-cigarettes and NRT (nicotine replacement therapy) products
- Health related quality of life (EQ-5D-5L & SF12)
- Physical activity (accelerometer) (7 days)
- Self-reported height and weight (BMI)
- Health service utilisation and costs, including smoking related costs
- Serious adverse event reporting

Participants who self-report that they have quit will be invited to attend a face-to-face assessment, which will include the following additional assessments:

- Self-reported prolonged abstinence (since last quit attempt, with date, if relevant)
- Expired carbon monoxide (CO) measurement

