16.6 Data handling and record keeping

Completed CRFs will be checked and signed at the collaborating University sites by a suitably qualified member of the research team before being sent to the CTU. Original CRF pages and questionnaires will be posted to the CTU at agreed timepoints with copies of the CRF retained at the relevant study site. Forms will be tracked using a web-based study management system. All data will be double-entered by the CTU on to a password-protected database. Double-entered data will be compared for discrepancies using a stored procedure and discrepant data will be verified using the original paper data sheets. Incomplete, incoherent, unreadable or other problem data in the CRF pages will be queried by the CTU with study site staff during data entry to ensure a complete and valid dataset. Questionnaire data will not be queried with participants. The CTU may complete further validation of data items, perform logical data checks and raise further data queries after data collection has been completed. The final export of anonymous data will be transferred to statisticians for analysis after all data cleaning duties have been performed by the CTU, this will usually be via email or a removable storage device. Identifiable information will not be exported from the study database as part of the final export.

Accelerometers will be received by the CTU and data will be downloaded and linked to participant ID numbers. Files will be checked before the accelerometers are recirculated. Files will be then further analysed with bespoke software to classify data into levels of physical activity intensity using accepted cut-points. Standard operating procedures will be applied to make a decision about dealing with missing data. Selected primary and secondary accelerometer derived outcomes will be merged into an individual participant data set, and securely stored as below.

Identifiable information will be omitted from the transcriptions of the process evaluation interviews.

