17.2 Statistical analysis

The reporting and presentation of this trial will be in accordance with the appropriate CONSORT guidelines [79, 80] and in line with the Russell Standard schedule [6], with the primary comparative analysis being conducted on an intention-to-treat basis. All comparative analyses will allow for potential clustering by site and/or GP surgery and/or trainer, adjusting for important baseline covariates of socioeconomic status and recent quit attempts as well as the other stratification factor 2-item Heaviness of Smoking Index (HSI) [74]. Further exploratory analysis will also account for partial clustering in the intervention group by research staff within each site.

For completeness, unadjusted between-group comparisons will also be presented, based on chisquared tests to compare binary outcomes (e.g. abstinence rates) and two sample t-tests to compare continuous outcomes (e.g. daily cigarette consumption) [74]. The between-group comparisons of smoking abstinence rates (and other secondary binary outcomes) will be expressed as odds ratios with 95% confidence intervals; the relative risk and corresponding confidence interval will also be presented as a more intuitive measure of the size of the intervention effect.

Where hypothesis tests are carried out, these will be at the 5% level for primary and secondary outcomes, and the 1% level for interaction terms. No adjustment for multiple analyses will be made; such adjustment methods are too conservative when outcomes are positively correlated, as they would be in this trial.

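### As written, follow-up BMI appears to use a newly self-reported height at each visit, which lowers the precision of the BMI comparison for no gain

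*Protocol*

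**What the plan says.** Protocol section 7.5 states: "At baseline, 3 and 9 months participants will be asked to self-report their height and weight". It continues: "Based on the weight and height reported we will derive a measure of BMI". The booklet contents in 10.1 (3 months) and 10.2 (9 months) and the schedule in 10.6 all list height together with weight at the follow-up visits. Nowhere does the protocol say that the baseline height is carried forward, or that each BMI must use the height from the same booklet.

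Three other statements bear on the point:

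- Section 16.6, on errors in the booklets: "Questionnaire data will not be queried with participants". The same section allows the CTU to run logical data checks.
- Section 17.2.4 analyses continuous secondary outcomes by linear regression "with adjustment for the stratification factors, important baseline covariates, and baseline outcome values, where relevant". Under 17.2, tests of secondary outcomes are at the 5% level.
- The relevant aim in section 6 is to find out whether the intervention "improves quality of life (SF 12, EQ-5D-5L), weight and cigarette cravings at 3 and 9 months post baseline". It names weight, not BMI.

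**The concern.** All participants are adults (section 8.4), so true height can be taken as fixed over 9 months. When someone reports 170 cm at baseline and 172 cm at 9 months, the difference is recall, rounding or unit conversion. BMI divides by height squared, so the discrepancy enters the outcome as an apparent change in BMI with no change in weight. Adjusting for baseline BMI does not remove error in a height reported afresh at follow-up, and discordant values will not be taken up with the participant.

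At stake is the precision of one secondary outcome. If height error is unrelated to arm, the estimated difference is still unbiased but its interval is wider than it need be.

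**Working it through.** The protocol gives no SD, effect size or power for BMI, so there is no figure to reproduce. What follows is an illustration on stated assumptions.

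**1. Effect of one wrong height.** BMI = weight / height². At 78 kg and 1.70 m, BMI = 78 / 2.89 = 26.99. With weight unchanged, a height reported too tall by 1, 2 or 3 cm moves BMI by −0.31, −0.62 or −0.93 kg/m².

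**2. Inputs for the variance calculation (none from the documents).** Mean BMI 27 (SD 5); mean height 1.70 m (SD 0.09 m); SD of true 9-month weight change 3.5 kg; weight-report error SD 1 kg per visit; height-report error SD σ per visit, with correlation ρ between visits.

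**3. One height at both visits.** The residual variance of 9-month BMI given baseline BMI is approximately

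(3.5² + 2 × 1²) / 1.70⁴ = 14.25 / 8.352 = 1.71.

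Simulation, which allows for the spread of heights, gives 1.76.

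**4. A new height at follow-up.** The added variance is approximately

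2(1 − ρ) × (2 × 27 / 1.70)² × σ², with σ in metres.

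For ρ = 0 this is 0.202, 0.807 and 1.816 for σ of 1, 2 and 3 cm. Divided by 1.71, these are increases of about 12%, 47% and 106%. For ρ = 0.9 they are one tenth of that.

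**5. Simulation of the baseline-adjusted regression (2 million people per row).**

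| Height-report error SD | ρ | Residual variance, one height | Residual variance, new height | Increase in variance | Increase in SE |
|---|---|---|---|---|---|
| 1 cm | 0 | 1.76 | 1.97 | 12% | 6% |
| 2 cm | 0 | 1.76 | 2.59 | 47% | 21% |
| 3 cm | 0 | 1.76 | 3.62 | 106% | 43% |
| 1 cm | 0.9 | 1.76 | 1.78 | 1% | 1% |
| 2 cm | 0.9 | 1.76 | 1.84 | 5% | 2% |
| 3 cm | 0.9 | 1.76 | 1.95 | 11% | 5% |

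**6. Sensitivity to the weight-report error.** Setting it to zero lowers the one-height variance to about 1.51. The increases with independent height errors become about 14%, 56% and 124%.

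**7. In terms of a detectable difference.** Section 10.4 expects 60–65% follow-up at 3 months; 65% of 450 is about 292 per arm. Take instead an SD of true BMI change of 1.5 kg/m² and independent height errors. The difference detectable with 80% power is then 0.348 kg/m² with one height, and 0.363, 0.408 or 0.472 kg/m² with a new height and error SD of 1, 2 or 3 cm.

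**The case against.** The strongest reply is that the protocol never says which visit's height goes into which BMI. Collecting height three times is not a rule to use three heights, and the sentence in 7.5 is compatible with one height throughout. A derivation rule of this kind can sit in the statistical analysis plan, which section 20.5 mentions and which is not at hand. This stands in part: that BMI is recalculated with each new height is the natural reading, not an express instruction. It is still worth settling, because every place that lists the item pairs height with weight at each visit and nothing points to a carried-forward height.

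Three further objections stand:

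- A reader might infer that the stated aim on weight is compromised. It is not: weight is reported at the same visits and does not depend on height.
- A reader might infer that the variance roughly doubles. That is the worst of the cases shown. People often repeat the same remembered height, and error that is the same at both visits contributes nothing to the visit-to-visit disagreement. With correlation 0.9 the loss is small.
- A reader might conclude that the repeat height question should be dropped. Since booklet entries are not queried with participants, a second height report is a useful check on a gross baseline error such as a unit slip.

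**Conclusion.** The point holds as a free improvement, not as an error that threatens the trial. On its natural reading, section 7.5 lets visit-to-visit disagreement in reported height into the BMI comparison. The cost is precision in one secondary outcome. There is no bias as long as height error is unrelated to arm, and the primary outcome, the sample size and the weight comparison are untouched.

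On the assumptions above, the loss runs from about 1% of residual variance (error SD 1 cm, correlation 0.9) to about 106% (error SD 3 cm, independent). The documents give nothing to place the trial within that range. Only the height component is removable: self-reported weight has its own error, which a fixed height leaves in place.

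**What to change.** Add one sentence to section 7.5, and carry the same rule into the statistical analysis plan: BMI at every visit is calculated from that visit's weight and a single height per participant, namely the baseline report, or a later report if the baseline value is missing or implausible. Define implausible in advance, without reference to trial arm.

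The repeat height question can stay as a consistency check. The change costs one derivation rule; it needs no new data and no change to the booklets.
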